8. ADVERSE EVENTS

8.1 Definitions

8.1.1 Adverse Event

The term **adverse event** covers any sign, symptom, syndrome, or illness that appears or worsens in a subject during the period of observation in the clinical study and that may impair the well being of the subject. The term also covers laboratory findings or results of other diagnostic procedures that are considered to be clinically relevant (e.g., that require unscheduled diagnostic procedures or treatment measures, or result in withdrawal from the study).

The adverse event may be:

- A new illness
- Worsening of a sign or symptom of the condition under treatment, or of a concomitant illness
- An effect of study medication, including test drug, placebo, and substances administered for clinical support with appropriate comment
- A combination of two or more of these factors
- No causal relationship with the study medication or with the clinical study itself is implied by the use of the term “adverse event”. Adverse events will be rated as definitely not drug related, probably not drug related, possibly drug related, probably drug related and definitely drug related, with information if test drug, concomitant therapy, underlying disease, study procedure may be involved.
- Surgical procedures themselves are not adverse events; they are therapeutic measures for conditions that require surgery. The condition for which the surgery is required may be an adverse event. Planned surgical measures permitted by the clinical study protocol and the condition(s) leading to these measures are not adverse events.

Illnesses first occurring or detected during the study such as recurrent infection or pneumonia are to be regarded as adverse events and must be documented as such in the CRF. Increase of mechanical ventilation support or changes in oxygenation will not be considered an adverse event, but the occurrence of pneumonia will be an adverse event.

Adverse events fall into the categories “non serious” and “serious” (see *Section 8.1.2 Serious Adverse Event*).

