7.2 Description of Study Days

7.2.1 General Recommendations and Procedures for Study

Test drug solutions (Azithromycin or placebo saline as required) will be prepared by the site pharmacist (see Section 5.3, 5.4 and Appendix C) in adequately labeled pouches transmitted to the investigator for storage at 5 °C or 41 °F until 1 hour prior to use. The temperature of the solution must be close to room temperature when infused. The same peristaltic pump should be used throughout the study. The exact

time of start and completion of the infusion will be recorded in the CRF, along with the volume infused (250 mL) and the label. It is not planned to collect retain samples pre or post infusion in this study. Efforts will be made to rotate infusion sites if a peripheral vein is used every 4th or 5th day, or more often in case of local signs. Preference will be given to a central line if available to ensure high blood flow.

Time (T=0) is always calculated from start of test drug infusion. Cannulae will be maintained patent with a slow saline infusion. No other drug may be infused concomitantly using the same i.v. line. A 24 hour time frame between daily infusions should be attempted.

Clearly a **hierarchy** for activities must be followed, collecting predrug (0 hr) samples (tracheal aspirate 1, blood safety, blood for WBC, blood gases, and blood culture if required etc.) or predrug information (vital signs i.e. blood pressure and heart rate, oxygenation, systemic and local tolerance, fever), all before initiating the test drug infusion. The precise time for starting and stopping the test drug infusion, for collecting tracheal aspirate 1 (predrug), aspirate 2 (~6 hours post infusion start), should be recorded in the CRF. ECG will be recorded 1 to 4 hours post infusion start as indicated in the appropriate study schedule and following recommendations of Appendix J. Fever will be measured in late afternoon (around 17:00 o'clock) and vital signs 6 hour post test drug infusion start (around 15:00 o'clock). Systemic and local tolerance will be observed throughout the study, until a week after cessation of therapy for adverse events for the former (i.e. Day n+7).

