8.1.2 Serious Adverse Event

A serious adverse event is one that at any dose:

- Results in death
- Is life-threatening
- Requires prolongation of hospitalization beyond anticipation due to underlying pathology and its expected complications
- Results in persistent or significant disability/incapacity
- Is a congenital anomaly/birth defect
- Represents overdose or false route of administration (even if no adverse event has occurred)

- Is medically important

A few terms are clarified below:

- A “life-threatening” condition implies that the subject was at immediate risk of death at the time of the serious adverse event but it does not refer to a serious adverse event that could have hypothetically caused death if it had been more severe
- A “persistent or significant disability or incapacity” implies a substantial disruption of a person’s ability to carry out normal life functions
- Medical and scientific judgment should be exercised in deciding whether other adverse events may be considered serious because they jeopardize the subject or may require intervention to prevent one of the other outcomes listed in the definition above. Examples of such events are intensive treatment for allergic bronchospasm, blood dyscrasias or convulsions. The List of Critical Terms (1998 adaptation of WHO Adverse Reaction Terminology Critical Terms List) should be used as guidance for adverse events that may be considered serious because they are medically important

All patients are expected to be in the ICU during the study and to remain in hospital for 2-4 weeks after study completion.

Cases involving cancer as an adverse event should be reported as “serious” using the criterion “medically important”.

Due to the patient population investigated, several fatal outcomes and serious adverse event are expected in this study.

Clarification of the difference in meaning between “severe” and “serious”:

The term “severe” is often used to describe the intensity (severity) of a specific event (as in mild, moderate, or severe myocardial infarction); the event itself, however, may be of relatively minor medical significance (such as severe headache). This is not the same as “serious”, which is based on the outcome or action criteria usually associated with events that pose a threat to life or functioning. Seriousness (but not severity) serves as a guide for defining regulatory reporting obligations.

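### The Section 8.1.1 exemption for ventilation support and oxygenation has no limit, so an acute respiratory deterioration without a diagnosis has neither AE nor SAE status

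*Protocol*

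**What the plan says.** Section 8.1.1 of the Protocol defines an adverse event broadly. Among the things that may be one are "Worsening of a sign or symptom of the condition under treatment, or of a concomitant illness" and "An effect of study medication, including test drug, placebo, and substances administered for clinical support with appropriate comment". It adds: "The term also covers laboratory findings or results of other diagnostic procedures that are considered to be clinically relevant", giving as examples findings that need unscheduled diagnostics or treatment, or that lead to withdrawal. New illnesses are kept in explicitly: "Illnesses first occurring or detected during the study such as recurrent infection or pneumonia are to be regarded as adverse events".

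The exemption comes next: "Increase of mechanical ventilation support or changes in oxygenation will not be considered an adverse event". The rest of that sentence keeps pneumonia as an adverse event and restores nothing else.

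Seriousness is then built on AE status. Section 8.1.1 continues "Adverse events fall into the categories" and names non-serious and serious. Section 8.1.2 lists the criteria for serious, including death, threat to life and medical importance. On medical importance it says: "Examples of such events are intensive treatment for allergic bronchospasm, blood dyscrasias or convulsions".

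On measurement, Section 7.2.1 has the site collect "predrug information (vital signs i.e. blood pressure and heart rate, oxygenation, systemic and local tolerance, fever), all before initiating the test drug infusion". Section 7.1.4 lists blood gases as safety data.

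**The concern.** In a ventilated patient, a fall in oxygenation or a need for more support is a direct sign that breathing has got worse. Most such changes will come from the underlying disease, and exempting routine fluctuations is sensible. The text does not stop there. It exempts the change whatever its size, whenever it starts and whatever the investigator suspects as the cause.

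Comparing the safety profile is a secondary objective (Section 2), and the drug is infused daily for up to 20 days. If a patient deteriorates acutely after an infusion and the blinded investigator cannot name a diagnosis, the sentence as written tells the investigator not to complete an AE form. The event then also misses the 24-hour serious-event notification in Section 8.3, which is how the sponsor would learn of an unexpected reaction while the trial is running.

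**Working it through.** No arithmetic applies. The check sets the passages side by side and follows the reporting rules through.

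**1. Exemption against the general definition (both in 8.1.1).** Take a fall in PaO2/FIO2 that needs more ventilatory support.

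| General definition | Does the event meet it? | After the exemption |
|---|---|---|
| Worsening of a sign | Yes | Not an AE |
| Effect of study medication | Yes, if that is the cause | Not an AE |
| Clinically relevant diagnostic result, such as one needing treatment | Yes | Not an AE |
| Illness first occurring or detected in the study | Only if an illness is identified | AE |

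The first three rows conflict. The fourth survives.

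**2. From AE to SAE.** Serious and non-serious are the two categories of adverse event in 8.1.1. A finding that is not an adverse event belongs to neither. So the threat-to-life and medical-importance criteria in 8.1.2 cannot be applied to an isolated desaturation, however severe.

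**3. Whether Section 8.3 rescues it.** Section 8.3 asks for events to be described as a diagnosis where possible and lets a non-specific sign stand in when there is none. That would normally cover an unexplained desaturation. The specific exemption closes this route for exactly these two signs.

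**4. Whether scheduled readings would show it.** For Days 1, 2 and 3, Section 7.2.3 lists blood gases and oxygenation under the procedures done before the infusion, and later days repeat those lists. The post-infusion lists give blood pressure, heart rate and respiration rate at about 6 hours after infusion start, with no blood gas or oxygenation reading. A fall that persists to the next morning would show in the next reading; a transient one would not. The Study Schedule table is not shown, so this rests on the text of Section 7.2.

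**5. Three illustrative cases under the rules as written.**
- *Bronchospasm is diagnosed after an infusion and treated intensively.* The diagnosis is an AE, and 8.1.2 gives it as an example of a serious one. It is captured.
- *The patient deteriorates and dies.* Death is a seriousness criterion in 8.1.2 and an efficacy variable in 7.1.1. It is captured.
- *Oxygenation falls sharply after an infusion, support is raised, no diagnosis is made, and values recover by the next morning.* There is no AE or SAE, and the fall does not appear in the scheduled blood gases or oxygenation.

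Only the third case is lost. It stays lost even if the investigator suspects the drug.

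**The case against.** The best defence is that a specific exception to a general definition is not in itself a contradiction. The sentence removes a support measure and a physiological reading, while the illness behind them stays reportable. Section 8.1.1 treats surgery the same way: the procedure is not an adverse event, but the condition requiring it may be. The bronchospasm example in 8.1.2 is a named diagnosis, which the exemption does not touch. That bronchospasm may first show as lower oxygenation is clinical background, not something the Protocol says.

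Much of this stands. The surgery analogy falls short at one point, however. The surgery text says in terms that the underlying condition may be an adverse event. The ventilation sentence says this only for pneumonia, and it is silent on deterioration that has no identified cause.

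A reader might go further and infer that acute respiratory harm is not recorded at all and never reported as serious. The documents do not support that. Blood gases are listed safety data (7.1.4) and are taken daily (7.2.3). Systemic tolerance is observed over 24 hours after each infusion, and each morning's list asks about events. New illnesses, diagnosed reactions and deaths remain reportable.

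Nor do patients who die or are extubated early vanish from the safety data because the clinical analysis requires a minimum treatment duration. Section 11.1 says all collected safety variables will be analysed, and the safety population in 11.2 is all randomized patients with at least one dose and interpretable data. The lack of a separate blood-gas paragraph in 11.3 is a matter for the detailed statistical plan announced there.

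**Conclusion.** The point holds in a limited form. The exemption in 8.1.1 is unqualified. It conflicts with the general AE definition in the same section, and it blocks the 8.1.2 seriousness criteria for one class of event: an isolated acute rise in ventilation support or change in oxygenation with no diagnosis attached. Such an event has no AE or SAE status even when it follows an infusion, is suspected to be drug related or is life-threatening. If it is transient, the pre-infusion readings will not show it either.

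The documents give no expected frequency for such events, so the size cannot be stated as a number. The conclusion assumes that sites apply the sentence literally and that the Study Schedule table, which is not shown, adds no post-infusion oxygenation reading. The second assumption affects only the point about transient falls; the loss of AE and SAE status does not depend on it. The matter does not touch the primary analysis. It is a worthwhile and inexpensive correction to safety reporting.

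**What to change.** Reconcile the passages in 8.1.1 and 8.1.2. Limit the exemption to routine ventilator adjustments and to oxygenation changes explained by the underlying disease. Add that any deterioration in ventilation or oxygenation that is suspected to be related to study drug, or that meets any 8.1.2 criterion, is recorded and reported as an AE or SAE, whether or not a diagnosis has been made.

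This needs about one sentence in 8.1.1 and no new measurement. The downside is some additional AE forms.

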8.1.2 Serious Adverse Event

A serious adverse event is one that at any dose:

- Results in death
- Is life-threatening
- Requires prolongation of hospitalization beyond anticipation due to underlying pathology and its expected complications
- Results in persistent or significant disability/incapacity
- Is a congenital anomaly/birth defect
- Represents overdose or false route of administration (even if no adverse event has occurred)

- Is medically important

A few terms are clarified below:

- A “life-threatening” condition implies that the subject was at immediate risk of death at the time of the serious adverse event but it does not refer to a serious adverse event that could have hypothetically caused death if it had been more severe
- A “persistent or significant disability or incapacity” implies a substantial disruption of a person’s ability to carry out normal life functions
- Medical and scientific judgment should be exercised in deciding whether other adverse events may be considered serious because they jeopardize the subject or may require intervention to prevent one of the other outcomes listed in the definition above. Examples of such events are intensive treatment for allergic bronchospasm, blood dyscrasias or convulsions. The List of Critical Terms (1998 adaptation of WHO Adverse Reaction Terminology Critical Terms List) should be used as guidance for adverse events that may be considered serious because they are medically important

All patients are expected to be in the ICU during the study and to remain in hospital for 2-4 weeks after study completion.

Cases involving cancer as an adverse event should be reported as “serious” using the criterion “medically important”.

Due to the patient population investigated, several fatal outcomes and serious adverse event are expected in this study.

Clarification of the difference in meaning between “severe” and “serious”:

The term “severe” is often used to describe the intensity (severity) of a specific event (as in mild, moderate, or severe myocardial infarction); the event itself, however, may be of relatively minor medical significance (such as severe headache). This is not the same as “serious”, which is based on the outcome or action criteria usually associated with events that pose a threat to life or functioning. Seriousness (but not severity) serves as a guide for defining regulatory reporting obligations.

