- Occurrence of *P. aeruginosa* pneumonia (primary variable)
The diagnosis of pneumonia will be assessed by an independent panel of experts under blinded conditions prior to stopping the study
- Occurrence of death (excluded if death within 3 days and not elicited by *P. aeruginosa*)
- Time to pneumonia (Day x), to exitus, or to bacteremia
- Time to extubation
- Overall outcome (until Day n+7)
- Duration of hospital and ICU stay
- Cost assessment
- Pa_{O2}/ FI_{O2}
- Occurrence of infections to other bacterial strain

Pharmacodynamic data

Tracheal aspirates (local laboratory, on Aspirate 1)

- Collection daily

- Quantitative culture for *P.aeruginosa* (CFU/mL) on Day -1, 1, 3, 6, 9, 12, 15, 18, and last day (i.e. Day x, or Day n-1, or Day 20)
- Isolate *P. aeruginosa* strain daily and store at -70°C on skim milk and glycerol
- Emergence of resistance (MIC to *P.aeruginosa* in tracheal aspirate for 11 standard antipseudomonal antibiotics on Day -1, and on last day (Day x, or Day 20, or Day n-1, or Day 20, see list Section 6.2)
- CFU for other strains from tracheal aspirates if indicated

BAL on Day x (or protected brush specimen (PBS), or aspirate local laboratory)

- Only for patients with suspected pneumonia to confirm diagnosis
- CFU/mL
- Cellularity

Tracheal aspirates (*in situ*, Geneva laboratory on Aspirate 2)

- Collection daily at study site, storage at -70°C prior to transfer to Geneva
 - Day -1, 1, 3, 6, 9, ..., last day (Day x, or Day n-1, or Day 20) for all patients
 - Daily for pneumonia (n=10) and control patients (n=20), selected on a site basis
 - Daily for patients under antibiotherapy
- Parameters
 - Content for autoinducer homoserine lactones: 3-oxo-C₁₂-HSL and C₄-HSL **and/or**
 - mRNA for LasB elastase (*lasI*, *rhlI*)

Respiration device on Day n-1 (Geneva laboratory)

- CFU/cm²
- Autoinducer content

Isolated *P.aeruginosa* strains from tracheal aspirate 1 and respiration device (Day n-1) (*in vitro*, Geneva laboratory)

- Day -1, 1, 3, 6, 9, ..., last day (Day x, or Day n-1, or Day 20) for all patients
- Daily for pneumonia (n=10) and selected control patients (n=20)
- Daily for patients under antibiotherapy
- *In vitro* virulence factor production (elastase, protease, rhamnolipids, cytotoxicity)
- *In vitro* autoinducer production (3-oxo-C₁₂-HSL and C₄-HSL)
- Azithromycin gradient plates for detection of rhamnolipid production (Day -1, Day x or Day n-1 or Day 20) to detect possible resistance mechanisms

Safety data

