5.2 Dosage Schedule

At each study site, the study medication will be prepared by the hospital pharmacist, using the method described in Appendix C, the randomization numbers allocated to the site and the randomization code provided by the independent statistician. The pouches will be infused i.v. by the investigator or his delegate, carefully following the procedures set out in this study protocol. Administration of study drug will be time zero, Day 1 (i.e. t=0 start of infusion) and the i.v. infusion will last 1 hour. Exact date, start

and completion time of infusion will be recorded daily in the case report form (CRF). If a central line is available, the study drug will be preferably infused by that port, avoiding any other concomitant infusion.

Efforts will be made to comply with a 24 hour interval between daily doses for a given patient throughout the treatment period as much as technically feasible. The maximum duration of treatment will be 20 days.

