7.1.1. Clinical efficacy data (collected at each clinical site)

Clinical efficacy (clinical site)

- Occurrence of *P. aeruginosa* pneumonia (primary variable)
The diagnosis of pneumonia will be assessed under blinded conditions by an independent panel of experts prior to stopping the study
- Occurrence of death (excluded if death within 3 days and not elicited by *P. aeruginosa*)
- Time to pneumonia, to exitus (Day -1), or to bacteremia
- Time to extubation (Day n-1)
- Overall outcome (until Day n+7)
- Duration of hospital and ICU stay
- Cost assessment
- PaO₂/ FI_{O2}
- Occurrence of infections to other bacterial strains

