7.2.5 Day n-1 (last day of treatment)

Day n-1 is the last day of treatment and corresponds to:

- Day of extubation due to improvement of patient condition. If a patient has to be re-intubated within 24 hours he will remain in the study and treatment with study drug continued daily until 2nd extubation successful or until Day 20 of treatment whatever happens first
- Exitus day
- Day 20: Treatment with study drug will be stopped even if ventilation will be continued

The required tests will correspond to Day 3 requirements with additional items for discharge unless not feasible:

- Adverse events from previous night
- Local tolerance
- Body temperature (tympanic or rectal) ~7:00
- Blood pressure, heart rate, respiration rate (~8:00)
- Blood gases
- Oxygenation: Pa_{O2}/ FI_{O2}
- Tracheal aspirate #1, collected pre last dose early morning if patient still ventilated for transfer to local laboratory for:
 - Quantification of *P. aeruginosa*
 - Isolation of *P. aeruginosa* strain and storage at -70°C
 - Special Day n-1 assessment for MIC on *P. aeruginosa* strain with 11 antipseudomonal antibiotics (listed under Section 6.2)
- ECG 1-4 hours post drug
- Lung X-ray whenever possible that day
- CPIS (use lung X-ray of same day)
- Clinical endpoints
- APACHE II score
- Tracheal aspirate #2 (for freezing at -70°C and transfer to Geneva laboratory for investigation), collected 6 hours post drug or earlier if extubation planned
- Extubate if applicable, if possible in the afternoon and after collection of tracheal aspirate sample 2, as medically indicated by weaning procedures
- Store ventilation device in sterile pouch at -70 °C, pending shipment to Geneva laboratory

In the case of exitus, the examinations performed on the previous day and on last third day (Day 9, 12, 15 etc.) will be used as Day n-1 values and the respiration device will be recovered and stored as described above.

On **Day n**, no study drug will be administered and the patient will be discharged from the study after physical examination and after collecting blood and urine safety samples. Ventilation will be continued if required.

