7.2.6 Poststudy (Day n + 7)

Information on the patient outcome (pneumonia, infection, strain, etc.) and intercurrent adverse events over the past week will be collected one week after cessation of therapy, i.e. on Day n+7, even for patients treated with antipseudomonal antibiotherapy, whether ventilated or not. This information will be best achieved by the treating physician visiting the patient at his present location or by obtaining a report.

The Quintiles study monitor will control the labeling, storage, and coordinate the shipment of all biological samples collected during the study by the ICU nurse to the University Hospital of Geneva, Switzerland. Shipment will be performed in batches of patients when convenient for site, monitor, and Geneva laboratory (see Appendix G).

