8.2 Period of Observation

For the purpose of this study, the period of observation extends from the time the subject gives informed consent until 7 days (Day n+7) after the last administration for tolerance and for clinical outcome.

If the investigator detects or learns about a serious adverse event in a study subject after the end of the period of observation, and considers the event possibly related to prior study treatment, he or she should contact the sponsor to determine how the adverse event should be documented and reported.

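### Hospital stay is an efficacy variable, but observation ends at Day n+7, before the protocol itself expects surviving patients to leave hospital

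*Protocol*

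**What the plan says.** The clinical efficacy list in Section 7.1.1, repeated in the synopsis, includes "Duration of hospital and ICU stay". It gives neither a start nor an end for the count. In the same list one item does carry an end: "Overall outcome (until Day n+7". Read beside it, the stay item looks like total stay.

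Three places set how long patients are followed:
- Section 7.2.5: on Day n, the day after the last treatment day, "the patient will be discharged from the study after physical examination and after collecting blood and urine safety samples".
- Section 7.2.6: information on outcome and adverse events "will be collected one week after cessation of therapy, i.e. on Day n+7". The examples of outcome given there are pneumonia, infection and strain. Discharge date is not among them.
- Section 8.2: "the period of observation extends from the time the subject gives informed consent until 7 days (Day n+7) after the last administration". It applies this limit to clinical outcome as well as to tolerance.

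After Day n+7, Sections 8.2 and 8.3 provide only for adverse events.

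Section 8.1.2 gives the expected course: "All patients are expected to be in the ICU during the study and to remain in hospital for 2-4 weeks after study completion".

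**The concern.** The protocol asks for a duration whose end it expects to fall outside the period it observes. If sites follow Sections 7.2.6 and 8.2 as written, most survivors will have no discharge date. What can be computed for them is time up to Day n+7, and that is set mainly by when study drug stopped.

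Study drug stops at extubation, death, pneumonia or Day 20, so the cut-off is not the same calendar point for everyone. It depends on the primary outcome. A stay measured this way would mix hospital use with treatment duration. The statistical analysis plan can choose a method for incomplete durations, but it cannot supply dates that were never collected. If no survivor's discharge is seen, a censored-data method has no discharges from which to estimate stay.

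**Working it through.** **Inputs**
- Expected stay after study completion: 2-4 weeks, that is 14 to 28 days (Section 8.1.2). This is the protocol's only figure on the point, and it computes nothing from it.
- End of observation: Day n+7 (Sections 7.2.6 and 8.2).
- Day n is the day after the last treatment day (Section 7.2.5). Since "The maximum duration of treatment will be 20 days" (Section 5.2), Day n is at most Day 21.
- Study completion is not defined, so three readings are tried: last dose (Day n-1), Day n and Day n+7.

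**Gap between end of observation and expected discharge**

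Gap = expected discharge day minus Day n+7.

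| Study completion read as | Expected discharge | Gap |
|---|---|---|
| Last dose (Day n-1) | Day n+13 to n+27 | 6 to 20 days |
| Day n | Day n+14 to n+28 | 7 to 21 days |
| Day n+7 | Day n+21 to n+35 | 14 to 28 days |

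Even the shortest expected stay outlasts observation on every reading. Section 8.2 equates Day n+7 with seven days after the last dose. Counted strictly from a last dose on Day n-1, that is Day n+6, and each gap grows by one day.

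**Part of the stay that is seen** (counting from Day 1, with completion at Day n)
- 20-day course, n = 21: days 1 to 28 are observed, out of 21+14 = 35 to 21+28 = 49. That is 28/35 = 80% down to 28/49 = 57%.
- 5-day course, n = 6 (the minimum before extubation for the efficacy population in Section 11.2): days 1 to 13 are observed, out of 6+14 = 20 to 6+28 = 34. That is 13/20 = 65% down to 13/34 = 38%.

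**Share of patients affected**

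Patients who die by Day n+7 have a complete stay. If all others follow the Section 8.1.2 expectation, share cut off = 1 - share dead by Day n+7. The protocol gives no overall mortality, so this is an assumed range:
- 4% dead (10% pneumonia × 40% mortality, from Sections 11.5 and 1.1): 96% cut off.
- 10% dead: 90%.
- 20% dead: 80%.
- 40% dead (the pneumonia mortality applied to everyone): 60%.

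**How the cut-off depends on the outcome**

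Under Section 7.2.4 a patient with pneumonia on Day x gets no further study drug and leaves the study on Day n, so Day n = x+1. Illustrations:
- Pneumonia on Day 5: Day n = 6, observed to Day 13. No pneumonia and ventilated through Day 20: Day n = 21, observed to Day 28. The patient with the complication has a window 28 - 13 = 15 days shorter.
- Pneumonia on Day 20: observed to Day 28. No pneumonia and extubated on Day 5: observed to Day 13. Now the patient with the complication has a window 15 days longer.

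Within one patient, pneumonia can only bring Day n forward. Between arms, the net effect depends on the mix of pneumonia and extubation times, so its direction cannot be predicted.

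**The case against.** The strongest reply is that the protocol never says stay is to be cut at Day n+7. The variable carries no limit, the closing rule in Section 8.2 sits in the adverse-event chapter, and the 2-4 weeks is an expectation mentioned in passing among the serious adverse event definitions. Sites could simply read the discharge date from the chart. The Study Schedule table and the case report form are not in the text at hand and might ask for it. This stands in part: the claim must be that no visible passage provides for the date, not that none exists. It does not remove the conflict, because the sections that govern follow-up stop clinical outcome at Day n+7.

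A reader might also infer more than the text supports:
- **ICU stay is cut off too.** Section 8.1.2 places patients in the ICU during the study and in hospital afterwards. It gives no length of ICU stay after Day n.
- **Cost inherits the fault.** "Cost assessment" is a separate, undefined item. Nothing says that it is built on hospital days.
- **The comparison is biased towards no difference.** The illustrations show that the window can be shorter or longer after pneumonia.
- **Nearly every patient is affected.** Deaths inside the window give complete stays, and Section 8.1.2 expects several fatal outcomes.
- **Recorded stay is just drug days plus a week.** That assumes counting from Day 1. Counting from admission adds earlier days, but the end is still missing.

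Finally, this is one secondary variable in a Phase IIa proof-of-concept study. The primary variable is untouched, and that limits the severity.

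**Conclusion.** The point holds for hospital stay. On the protocol's own expectation, a survivor's discharge falls 7 to 21 days after observation ends if completion is Day n, and 6 to 28 days across all three readings. It rests on the Section 8.1.2 expectation being roughly right and on the unseen Study Schedule containing no later discharge field. The share of all patients cut off, 60% to 96%, rests on assumed mortality and should be read only as a range. Because the cut-off moves with the primary outcome, the between-arm comparison of stay can be distorted in a direction that cannot be predicted. ICU stay and cost are not shown to be affected in the same way. Severity is low to moderate.

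**What to change.** In Sections 7.2.6 and 8.2, have sites record from the hospital chart the hospital discharge date, the ICU discharge date, or death, up to a stated fixed day counted from randomization. That day should be the same for all patients, so that the limit no longer depends on when treatment stopped. The latest discharge the protocol expects is Day 21+28 = 49 (completion at Day n) or Day 21+35 = 56 (completion at Day n+7), so a limit such as Day 60 would cover it. Treat patients still in hospital at the limit as censored, and state the day from which stay is counted. Keep death distinct from discharge alive, so that an early death is not counted as a short stay.

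If the sponsor does not want these dates, remove total hospital stay from the efficacy variables in Section 7.1.1 and the synopsis.

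The cost is a few case report form fields filled from existing records, with no extra patient contact, and a database lock a few weeks later for the last patients.
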